# 8.2.2 Additional Eligibility Criteria for the Treatment With MOR03087, Dexamethasone and Lenalidomide

#### **Inclusion Criteria**

- 1. Documented diagnosis of MM; specifically, relapsed or refractory MM defined as:
  - Received at least one previous therapy
  - All subjects must have documented progression during or after their last prior therapy for MM
- 2. Ability to understand the reason for and understand the special conditions of the pregnancy prevention risk minimization plan and give written acknowledgement of these

- 3. Ability and willingness to comply with the special conditions of the pregnancy prevention risk minimization plan
- 4. Creatinine clearance  $\geq$  50 mL/min (calculated using the Cockcroft-Gault equation)
- 5. Platelets:
  - $\geq$  75 × 10⁹/L for subjects in whom < 50% of bone marrow nucleated cells are plasma cells
  - $\geq$  30 × 10⁹/L for subjects in whom  $\geq$  50% of bone marrow nucleated cells are plasma cells.

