# 8.2.3 Additional Eligibility Criteria for the Treatment With MOR03087, Dexamethasone and Pomalidomide

#### Inclusion Criteria

- 1. Documented diagnosis of MM; specifically, relapsed and refractory MM defined as:
  - Received at least two previous therapies including LEN and a proteasome inhibitor
  - All subjects must have documented progression during or within 60 days after their last prior therapy for MM
- 2. Ability to understand the reason for and understand the special conditions of the pregnancy prevention risk minimization plan and give written acknowledgement of these
- 3. Ability and willingness to comply with the special conditions of the pregnancy prevention risk minimization plan
- 4. Creatinine clearance  $\geq$  45 mL/min (calculated using the Cockcroft-Gault equation)
- 5. Platelets:
  - $\geq$  75 × 10⁹/L for subjects in whom < 50% of bone marrow nucleated cells are plasma cells
  - $\geq 30 \times 10^9/L$  for subjects in whom  $\geq 50\%$  of bone marrow nucleated cells are plasma cells

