# 8.5 Dose Limiting Toxicities

Adverse events will be graded according to NCI CTCAE, version 4.0, with a DLT being defined as an AE assessed as having a suspected or unknown relationship to the study drug (MOR03087, POM, or LEN) and meeting one of the following criteria:

- Non-hematologic DLT:
  - o Liver

Any grade 3 AST/ALT that does not resolve to grade 1 within 14 days or any grade 4 elevation in liver function tests (AST/ALT)

- Gastrointestinal
  - $\geq$  Grade 3 vomiting or nausea despite the use of standard antiemetics

Sponsor: MorphoSys AG

- $\geq$  Grade 3 diarrhea or constipation despite the use of optimal treatment
- All other events
  - ≥ Grade 3 (excluding hypersensitivity reactions and fatigue)
- Hematologic DLT:
  - Grade 4 thrombocytopenia that requires more than one platelet transfusion and does not resolve to grade 2 or less within 14 days
  - Grade 4 neutropenia that does not resolve to grade 2 or less within 14 days
  - Or any other grade 4 hematologic toxicities that do not resolve to grade 2 or less within 14 days and that are considered clinically relevant by the investigator
- Any AE that delays treatment with study drug for more than 14 days

In addition, any event will only qualify as a DLT if a worsening of the event from baseline of at least 2 CTCAE Grades occurs.

The DLTs for the POM combination cohorts are specified as above except for the hematological DLTs which are as follows:

- Hematologic DLT:
  - Grade 4 neutropenia for > 7 days
  - Febrile neutropenia (ANC <1000/mm³ with a single temperature of >38.3°C or a sustained temperature of  $\geq$  38°C for more than 1 hour)
  - o Thrombocytopenia
    - Platelet count  $< 25,000/\mu$ L that requires more than one platelet transfusion or
    - Platelet count  $\ge 25,000/\mu L$  to  $< 50,000/\mu L$  with significant bleeding (defined as need for hospitalization and/or platelet transfusion)
  - Or any other grade 4 hematologic toxicities that do not resolve to grade 2 or less within 14 days and that are considered clinically relevant by the investigator

The DLTs for the LEN combination cohorts are specified as above except for the hematological DLTs which are as follows:

- Hematologic DLT:
  - Grade 4 neutropenia for > 7 days
  - Febrile neutropenia (ANC <1000/mm³ with a single temperature of >38.3 °C or a sustained temperature of  $\geq$  38 °C for more than 1 hour)
  - o Thrombocytopenia

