    - Platelet count  $< 30,000/\mu$ L that requires more than one platelet transfusion or
    - Platelet count  $\ge$  30,000/µL to < 50,000/µL with significant bleeding (defined as need for hospitalization and/or platelet transfusion)
  - Or any other grade 4 hematologic toxicities that do not resolve to grade 2 or less within 14 days and that are considered clinically relevant by the investigator

The DLT period covers Day 1 of cycle 1 (starting with first study drug administration) until Day 29 (before start of the second cycle). Granulocyte-colony stimulating factor (GCSF) therapy is prohibited during this time.

Laboratory DLTs will be reported as AEs.

Sponsor: MorphoSys AG

Confidential

Subjects experiencing DLTs in the study should not receive further study drug.

If upon treatment with POM or LEN, subjects present with protocol-defined DLTs or toxicities or conditions described in the corresponding Section 9.1.4, treatment must be modified or interrupted accordingly.

If upon treatment with DEX, subjects present with protocol-defined toxicities or conditions described in the corresponding SmPC, treatment must be modified or interrupted accordingly.

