- A subject is withdrawn at the specific request of the sponsor in case of serious safety concerns.
- A subject is treated with another monoclonal antibody.
- A subject requires different myeloma-specific treatment due to progressive disease.

Subjects who receive specific anti-myeloma treatment other than those specified in the protocol should be withdrawn from the study.

Subjects who withdraw whilst their safety assessment period is not evaluable will only be replaced during the dose-escalation phase until the applicable cohort consists of a sufficient number of evaluable subjects. However, withdrawals due to DLTs will not be replaced.

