# 9.1 Investigational Medicinal Products

# 9.1.1 MOR03087

# Laboratory Evaluations prior to each Administration of MOR03087

For all administrations of MOR03087, the following parameters should be taken pre-dose on the day of study drug administration and, if outside the limits described below, administration of MOR03087 should be postponed (see Section 8.6):

Value	Subject should not be dosed with MOR03087 if the value is:
Creatinine	> 3 × ULN
Hemoglobin	< 8.0 g/dL (subject should be transfused before dosing)
Platelets	$< 25.0 \times 10^{9}$ /L (< 30.0 × 10 ⁹ /L in the LEN and POM parts)
WBC	$< 1.0 \times 10^{9}/L$
Potassium	> 6.0 mmol/L
Sodium	> 155 mmol/L
AST/ALT	$> 3 \times ULN$

POM, LEN or DEX might have to be interrupted and/or dose reduced as well according to Section 9.1.4.

MOR03087 is a fully human monoclonal antibody targeting the CD38 membrane protein. It is presented as a clear to slightly opalescent, slightly yellowish sterile solution for injection formulated in a histidine buffer at pH 6.8, with sodium chloride (NaCl) and Tween20. MOR03087 will be provided in a labelled 10R glass vial at a concentration of 8-12 mg/mL with an extractable volume of 5 mL (40 mg/vial-60 mg/vial). The appropriate number of vials will be supplied to each respective site. Four vials will be packed in 1 drug box. MOR03087 must be stored at -20°C  $\pm$  5°C. The drug has to be obtained from the freezer between 3 days to 16 hours before the planned start of the infusion to allow for the preparation of the infusion. The drug has to be thawed as well as stored at 2-8°C until the preparation for infusion. MOR03087 will be diluted in 100 mL or 250 mL as appropriate with commercially available 0.9% NaCl saline (Ecoflac® plus from B. Braun) for injection and will be provided by the sponsor.

The individual MOR03087 infusion will be prepared at the site, according to directions of the sponsor, which will be laid down in a drug preparation manual. It will be administered by slow intravenous (IV) infusion over approximately 2 hours. If any given infusion is well tolerated and could be administered without any infusion reaction, the subsequent infusion should be administered with the next shortest infusion duration according to the following steps: 90 min.,

60 min., 45 min., 30 min. (scheme in Table 3). Infusion duration should not be shorter than 30 minutes.

[figure not shown]

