#### Table 5LEN Dose Modification Instructions for Toxicities

Toxicity	LEN Dose Modification
Neutropenia (ANC < 0.5 x 10 ⁹ /L)	Stop LEN dosing and follow hematology weekly. If the subject was not receiving GCSF therapy, GCSF therapy may be started at the discretion of the treating physician. When ANC returns to $\geq 0.5 \times 10^{9}$ /L, LEN dosing may be restarted at same dose level if neutropenia was the only DLT and GCSF treatments are continued, or decreased by one dose level. Note: GCSF is prohibited during Cycle 1
Thrombocytopenia (Platelets <30 x10 ⁹ /L)	Stop LEN dosing and follow hematology weekly. When platelets return to $\geq 30 \times 10^9$ /L, resume LEN dosing at one dose level lower

Toxicity	LEN Dose Modification
Rash	
 
Grade 2-3 skin rash: LEN interruption or discontinuation should be considered at the discretion of the treating physician.
 
Angioedema, Grade 4 rash, exfoliative or bullous rash or if Stevens-Johnson syndrome (SJS) or toxic epidermal necrolysis is suspected, LEN must be discontinued permanently
 

Other $\geq$ Grade 3 LEN-related adverse events	Stop LEN dosing and restart at one dose level lower when toxicity has resolved to $\leq$ Grade 2 at physician's discretion.

ANC: absolute neutrophil count; DLT: dose limiting toxicity; GCSF: granulocyte colony-stimulating factor; LEN: lenalidomide

LEN should be discontinued if the subject is unable to tolerate the lowest dose level. At the discretion of the investigator, the treatment with MOR03087 and dexamethasone may be continued.

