# 9.1.4.2 POM Dose Modification

Subjects will be evaluated for AEs at each visit with the NCI CTCAE version 4.0 as a guide for the grading. Interruptions and reductions are permitted throughout the study.

Table 6 outlines the dose reduction steps for POM. Instructions for dose interruptions and reductions for POM are outlined in Table 7 (hematologic and non-hematologic toxicities).

Table 6Pomalidomide Dose Reduction Steps by Dose Level

Dose Level (Days 1-21 of 28 days)	POM Dose Reduction (Days 1-21 of Every 28-Day Cycle)
Starting dose	4 mg
Dose Level -1	3 mg
Dose Level -2	2 mg
Dose Level -3	1 mg ¹

POM: pomalidomide

¹ The POM treatment regimen should be discontinued if the subject cannot tolerate the 1 mg dose.

Table 7	Pomalidomide Dose Modification Instructions for Toxicities

Toxicity	POM Dose Modification
Neutropenia ANC < $0.5 \ge 10^{9}$ /L) or Febrile neutropenia (fever $\ge 38.5$ °C and ANC < $1.0 \ge 10^{9}$ /L)	Hold POM dosing and follow hematology weekly. If the subject was not receiving GCSF therapy, GCSF therapy may be started at the discretion of the treating physician. When ANC returns to $\geq 0.5 \ge 10^{9}$ /L, restart POM dosing at one dose level lower. Note: GCSF is prohibited during Cycle 1
Thrombocytopenia (Platelets < 25 x 10 ⁹ /L)	Hold POM dosing and follow hematology weekly. POM dosing may resume at one dose level lower once the platelet count has recovered to $\geq 50,000/\mu$ L.
Other $\geq$ Grade 3 POM-related toxicities	Interrupt POM dosing and restart at one dose level lower when toxicity has resolved to $\leq$ Grade 2 at the physician's discretion

ANC: absolute neutrophil count; GCSF: granulocyte colony-stimulating factor; POM: pomalidomide

To initiate a new cycle of POM, the neutrophil count must be  $\ge 0.5 \ge 10^9/L$  with or without GCSF, the platelet count must be  $\ge 50 \ge 10^9/L$ .

POM should be discontinued if subject is unable to tolerate the lowest dose level. At the discretion of the investigator, the treatment with MOR03087 and dexamethasone may be continued.

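### In Part E, and probably Part D, a subject entering with platelets of 30 to below 50 × 10⁹/L cannot have a platelet fall qualify as a DLT short of death, and such events are filtered in a direction that favours passing the dose

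*Protocol*

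**What the plan says.** **Entry.** Protocol 8.2.2 (LEN) and 8.2.3 (POM) set a platelet floor of 75 × 10⁹/L. It drops to "30 × 10⁹/L for subjects in whom" at least half "of bone marrow nucleated cells are plasma cells".

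**DLT clauses.** For Parts D and E, 8.5 replaces the general hematologic list with count-based platelet clauses (all counts × 10⁹/L):
- Transfusion clause: a count below 25 (POM) or below 30 (LEN) "that requires more than one platelet transfusion or", as the alternative,
- Bleeding clause: a count from that limit to below 50 with bleeding that needs hospital admission or platelet transfusion.

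**Baseline condition.** 8.5 also states that "any event will only qualify as a DLT if a worsening of the event from baseline of at least 2 CTCAE Grades occurs". The POM and LEN definitions carry over everything except the hematologic list, and no exemption for a low baseline is given.

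**Handling of a fall.** Below 30 in the LEN and POM parts, "administration of MOR03087 should be postponed" (9.1.1). LEN stops below 30, and on recovery the site is to "resume LEN dosing at one dose level lower" (Table 5). POM is held below 25 and also resumes one level down (Table 7). Section 15.1 removes from the DLT Evaluable Population anyone whose LEN or POM dose is modified in Cycle 1 for a non-DLT reason. Under 8.7.1, non-evaluable subjects "will only be replaced during the dose-escalation phase until the applicable cohort consists of a sufficient number of evaluable subjects".

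**The concern.** The entry floor and the baseline condition do not fit together. A subject admitted at grade 3 has only grade 4 and death left, so a two-grade worsening of the count means death. Section 7.3 names thrombocytopenia as the earliest effect expected on non-tumor cells and says an additive effect with LEN or POM cannot be excluded. The insensitive spot therefore falls on a toxicity that the escalation is meant to detect.

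At stake is the DLT count behind a primary endpoint. SAP 10.1 puts the MTD below a level with 2 DLTs in 3 or in 6 subjects, and Protocol 7.1 expands a cohort at 1 in 3. One filtered event can make 1/3 read as 0/3, or 2/6 as 1/6. Alternatively it removes the subject from the denominator.

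**Working it through.** The plan gives no figure on this point. Its only probability statement (Protocol 15.9, nine subjects) reproduces: 1 − 0.83⁹ = 0.813 and 1 − 0.77⁹ = 0.905, against 81% and 90%. Nothing below depends on it.

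**Inputs.** The entry floors are from 8.2.2 and 8.2.3, the clauses and the two-grade rule from 8.5, and grade 5 = death from 12.1. Assumed platelet bands (× 10⁹/L): grade 2 is 50 to below 75, grade 3 is 25 to below 50, grade 4 is below 25.

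**Can a count qualify?** For each whole-number baseline and each count at or below it that falls in a clause, require grade(count) − grade(baseline) ≥ 2.

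| Entry platelets | Part D, transfusion clause | Part D, bleeding clause | Part E, transfusion clause | Part E, bleeding clause |
|---|---|---|---|---|
| 30 to <50 | 0 of 500 | 0 of 310 | 0 of 600 | 0 of 210 |
| 50 to <75 | 625 of 625 | 0 of 625 | 625 of 750 | 0 of 500 |
| 75 to <150 | 1875 of 1875 | 1875 of 1875 | 2250 of 2250 | 1500 of 1500 |

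For the first cell, 20 baselines × 25 counts (0 to 24) = 500 pairs, each grade 3 to grade 4, a rise of 1. The cells count combinations; they are not probabilities. A fall from 40 to 20 with two transfusions satisfies the wording of the transfusion clause in both Parts, but does not qualify as a DLT.

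**Sensitivity to the assumed bands.**
- Grade 3/4 limit at 20 or 30: still 0 in every cell of the first row.
- Grade 2/3 limit at 40: the closed entry range shrinks to 30 to <40.
- Grade 2/3 limit at 30: the transfusion clause opens (500 of 500 in Part D, 500 of 600 in Part E); the bleeding clause stays at 0.

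**What happens to a transfusion-clause event that fails only the two-grade rule?** Section 15.1 requires at least 16 unmodified LEN or POM doses and at least 4 weekly-schedule MOR03087 doses.
- LEN or POM doses taken before each scheduled count: Day 2, 1; Day 4, 3; Day 8, 7; Day 15, 14. All are below 16. The drug is held and then stepped down for a reason that is not a DLT, so the subject is excluded and, during escalation, replaced.
- Before the Day 22 count: 21 LEN or POM doses, and 4 MOR03087 doses (Days 1, 4, 8, 15). Both minimums are met. Whether the subject stays evaluable and DLT-free depends on whether the later step-down counts as a modification required within Cycle 1, which 15.1 does not settle.

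**Part D.** Section 9.1.4.2 sets a condition for starting a new POM cycle: "with or without GCSF, the platelet count must be" at least 50 × 10⁹/L. If that covers Cycle 1, a subject at 30 to <50 cannot start POM, which contradicts 8.2.3. Its place under dose modification suggests Cycle 2 onward, but the text does not say so. Part E has no such threshold.

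**The case against.** **The rule may not reach the count clauses.** The two-grade sentence stands before the Part D and E lists, which use absolute counts; the LEN limit of 30 is not a grade boundary on the assumed bands. The clauses could be read as free-standing. That reading is possible, but the rule covers any event and only the hematologic list is replaced, so it is the less natural one. The ambiguity is itself a reason to clarify 8.5.

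**Safeguards exist.** The DMC considers first-cycle AEs (Protocol 7.1) and exclusion reasons are compiled before each review (SAP 8.2). A sponsor or DMC field overrides the investigator's DLT tick (SAP 10.1), and the recommended dose may be set below the MTD. This stands and reduces the effect, although no written rule directs anyone to use the field for these events.

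**Excluded subjects are not counted as DLT-free.** This is true for falls seen by Day 15, but exclusion and replacement still take a drug-related toxicity out of the DLT count.

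**Stronger readings that the documents do not support.** A reader might infer that:
- no output anywhere would show these events. That cannot be said: SAP section 13, the list of tables and listings, is blacked out, and the separate Statistical Interim Safety Analysis Plan was not supplied. The first-cycle AE tables, hematology shift tables and exclusion listing would contain them; the readable text simply describes none that singles them out.
- no thrombocytopenic complication in these subjects can be a DLT. A new bleed of grade 3 or more can still qualify in its own right under the non-hematologic criteria.

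**Conclusion.** The concern holds as a minor point. On the natural reading of 8.5 and the assumed bands, a Part E subject entering at 30 to <50 × 10⁹/L cannot have a platelet-count event qualify under either platelet clause short of death. The same holds in Part D unless the POM start threshold covers Cycle 1. The transfusion-clause result depends on where grade 3 begins. Exclusion by Day 15 follows from the rules; the Day 22 route to a DLT-free count is possible but not certain.

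Both routes lean towards passing the dose. It would go too far to infer a known bias in the MTD: the documents give no baseline platelet distribution and no event rates, so the effect cannot be computed. The affected group is narrow: at least 50% marrow plasma cells, a low entry count and a drug-related event in Cycle 1, within Parts of up to 18 subjects each. Escalation is also judged by the DMC rather than applied mechanically.

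**What to change.** **Protocol 8.5.** Keep the two-grade rule, which sensibly guards against calling disease-related cytopenia a DLT. Add that a Part D or E subject with baseline platelets below 50 × 10⁹/L, whose event meets a platelet clause and fails only that rule, is not counted as DLT-free. The event goes to the DMC for adjudication before any exclusion or replacement. State whether the bleeding clause is graded on the count or on the bleed. The same edit can settle whether the POM start threshold covers Cycle 1 and whether a step-down after Day 22 counts as a Cycle 1 modification.

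**SAP 10.1 and the DMC output.** Unless section 13 or the interim safety plan already provides it, list each filtered event with baseline count, nadir, number of transfusions and bleeding.

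**Cost.** A few sentences and one listing; platelet counts and transfusions are already recorded. A few disease-related falls will need adjudication, and an occasional extra subject may be needed in escalation.

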- Severe: Incapacitating (causes inability to perform usual activity or work)

The toxicity grade of AEs will be graded according to the NCI CTCAE (version 4.0 of May 28, 2009) using the following definitions:

- Grade 1: Mild; asymptomatic or mild symptoms; clinical or diagnostic observations only; intervention not indicated.
- Grade 2: Moderate; minimal, local or non-invasive intervention indicated; limiting age-appropriate instrumental activities of daily living (refers to

preparing meals, shopping for groceries or clothes, using the telephone, managing money, etc.).

- Grade 3: Severe or medically significant but not immediately life-threatening; hospitalization or prolongation of hospitalization indicated; disabling; limiting self-care activities of daily living.
- Grade 4: Life-threatening consequences; urgent intervention indicated.
- Grade 5: Death related to AE.

The causal relationship of all AEs to IMP intake will be judged as either suspected or not suspected. If no relationship has been provided by the investigator, the event will be considered as related to study drug and notified to authorities according to regulatory reporting requirements.

In addition to the investigator's own description of the AEs, each AE will be encoded by the sponsor (or its delegate) according to the current version of the Medical Dictionary for Regulatory Activities (MedDRA).

All non-serious AEs must be followed up for a final outcome until resolution or until the EOS visit. An outcome of "unknown" is not considered to be an acceptable final outcome. An outcome of "not yet resolved" is an acceptable final outcome for non-serious AEs at the end of a subject's participation in a study. SAEs must be followed up for a final outcome until resolution or, if resolution becomes unlikely, until stabilization or death. This includes obtaining information on recovery and any sequelae and, in case of a fatal outcome, the cause of death. For SAEs which are due to progression of MM, follow-up only until the end of subject's participation in the study is acceptable.

will report all reportable events to all competent authorities (including the European Medicines Agency [EMA]), IECs or Institutional/Independent Review Boards (IRBs), and investigators as required by local regulations and Premier Research standard operating procedures (SOPs).

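### In Parts D and E, a bleed below Grade 3 that needs exactly one platelet transfusion can be a DLT at the higher platelet count but not at the lower one

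*Protocol*

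**What the plan says.** Protocol section 8.5 (repeated in the synopsis under Special Safety Assessments) keeps the general non-hematologic and treatment-delay criteria for Parts D and E and replaces the hematologic ones. For platelets there are two bullets in each combination:

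- Below 25,000/µL (POM) or 30,000/µL (LEN): a count "that requires more than one platelet transfusion or", where the last word leads into the next bullet. Bleeding is not mentioned.
- From that cut-off to below 50,000/µL: a count "with significant bleeding (defined as need for hospitalization and/or platelet transfusion").

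Three other provisions of 8.5 bear on the point. Other non-hematologic events count from Grade 3 upward, apart from hypersensitivity reactions and fatigue. An AE that delays study drug by more than 14 days counts. And "any event will only qualify as a DLT if a worsening of the event from baseline of at least 2 CTCAE Grades occurs".

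A DLT has a fixed consequence: "Subjects experiencing DLTs in the study should not receive further study drug". A low platelet count that is not a DLT is handled differently. In Table 5, LEN stops below 30 × 10⁹/L; on recovery to that level the instruction is to "resume LEN dosing at one dose level lower". In Table 7, POM is held below 25 × 10⁹/L, and "POM dosing may resume at one dose level lower once the platelet count has recovered to" 50,000/µL. Section 9.1.1 also postpones MOR03087 below 30 × 10⁹/L in these parts.

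**The concern.** A toxicity rule should not become more lenient as the toxicity gets worse. Here the same bleed with the same single transfusion counts at 40,000/µL and does not count at 15,000/µL. The plan gives no reason for this.

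The DLT count in 3 to 6 evaluable subjects per cohort feeds escalation and the MTD (Protocol 7.1, SAP 10.1). Platelets are also where this drug is expected to act: Protocol 7.3 names thrombocytopenia as the earliest expected effect on non-tumor cells and cannot exclude an additive effect with LEN or POM. An uncounted event at a low platelet count pushes the assessment toward tolerability.

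The subject may also leave the denominator. A Cycle 1 change of LEN or POM dose for a reason other than a DLT removes the subject from the DLT Evaluable Population (Protocol 15.1, SAP 6). During dose escalation that subject is then replaced (Protocol 8.7.1, SAP 8.2).

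**Working it through.** **The plan's own figure.** The only probability the plan computes is in Protocol 15.9, for seeing an AE at least once in 9 subjects: 1 − 0.83⁹ = 0.813 and 1 − 0.77⁹ = 0.905, against 81% and 90% stated. It reproduces, but has no bearing on the DLT wording.

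**Applying the rule.** Take a drug-related Cycle 1 bleed below Grade 3, no hospitalization, no delay over 14 days, platelets recovered within 14 days, 2-grade rule met:

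| Platelets (/µL) | Part D, 1 transfusion | Part D, 2 | Part E, 1 transfusion | Part E, 2 |
|---|---|---|---|---|
| 15,000 | no DLT | DLT | no DLT | DLT |
| 24,999 | no DLT | DLT | no DLT | DLT |
| 25,000 | DLT | DLT | no DLT | DLT |
| 29,999 | DLT | DLT | no DLT | DLT |
| 30,000 | DLT | DLT | DLT | DLT |
| 40,000 | DLT | DLT | DLT | DLT |

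The inversion arises only with exactly one transfusion. If the 2-grade rule is not met, the event is not a DLT in either band. That may apply to subjects admitted with platelets from 30 × 10⁹/L (Protocol 8.2.2, 8.2.3). The residual Grade 4 clause does not close the gap: it covers other hematologic toxicities, and only if unresolved at 14 days and judged clinically relevant.

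**Where the subject goes.** Usually the LEN or POM hold and step-down makes the subject non-evaluable. With onset on Days 22–28 no LEN or POM is due. By then a subject on schedule has had 21 doses (minimum 16) and at least 4 MOR03087 infusions (Days 1, 4, 8, 15; minimum 4). If a step-down first applied in Cycle 2 is not read as a first-cycle modification, the subject stays evaluable without a DLT.

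**Size.** A level passes with 0 of 3 DLTs, or 1 of 3 followed by 0 of 3 (Protocol 7.1, SAP 10.1). At a per-subject rate r:

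P(r) = (1 − r)³ + 3r(1 − r)² × (1 − r)³

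Let d be the rate of all other DLTs and x the rate of the uncounted event. Both are assumptions.

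- Counted as a DLT: r = d + x
- Excluded and replaced: r = d/(1 − x)
- Counted as no DLT: r = d

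For d = 0.20 and x = 0.01:

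- r = 0.21: 0.493 + 0.194 = 0.687
- r = 0.20/0.99 = 0.202: 0.508 + 0.196 = 0.704
- r = 0.20: 0.512 + 0.197 = 0.709

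| d | x | Counted | Excluded | No DLT | Excess, excluded / no DLT (points) |
|---|---|---|---|---|---|
| 0.10 | 0.005 | 0.898 | 0.905 | 0.906 | 0.8 / 0.8 |
| 0.10 | 0.01 | 0.889 | 0.904 | 0.906 | 1.5 / 1.7 |
| 0.20 | 0.005 | 0.698 | 0.706 | 0.709 | 0.9 / 1.1 |
| 0.20 | 0.01 | 0.687 | 0.704 | 0.709 | 1.7 / 2.2 |
| 0.30 | 0.005 | 0.484 | 0.491 | 0.494 | 0.7 / 1.0 |
| 0.30 | 0.01 | 0.474 | 0.488 | 0.494 | 1.4 / 2.0 |

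The excess is taken from unrounded values.

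**The case against.** The strongest reply is that the uncovered event may hardly exist. By the generic grades in Protocol 12.1, Grade 2 is limited to "minimal, local or non-invasive intervention indicated", and Grade 3 includes "hospitalization or prolongation of hospitalization indicated". An investigator may well grade a transfused bleed as 3, which makes it a DLT at any count, subject to the 2-grade rule. This largely stands. The organ-specific bleeding grades are not in the documents, so how many transfused bleeds stay below Grade 3 cannot be settled. It is tempting to answer that the upper-band bleeding criterion would then be redundant, but its hospitalization half already overlaps with Grade 3, so redundancy in this list proves little.

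Second, a low count holds both MOR03087 and LEN or POM, and POM waits for 50,000/µL. The 14-day delay criterion can therefore catch some of these events. This also stands, but only for longer delays.

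Third, the DMC reviews reported AEs before each new cohort, the recommended dose rests on all available safety data, and a sponsor or DMC decision overrides the investigator's DLT entry (Protocol 15.7.1, SAP 10.1). These can correct single cases. They are discretionary and leave the written criterion unchanged.

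Fourth, escalation in Parts D and E is at most 12 + 12 subjects. At 0.5–1% that is 24 × 0.005 = 0.12 to 24 × 0.01 = 0.24 expected events, with a chance of none between 0.99²⁴ = 79% and 0.995²⁴ = 89%. This is why the point is minor.

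**Conclusion.** The inversion is in the current text of both combinations and no other clause removes it. It is confined to a related Cycle 1 bleed graded below 3, with exactly one transfusion, no hospitalization, no delay over 14 days and the 2-grade rule met.

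At an assumed event rate of 0.5–1% and a 20% rate of other DLTs, the pass probability is about 1–2 percentage points too high; with other-DLT rates of 10–30% the range is 0.7–2.2 points. The event rate cannot be derived from the documents. The excluded-and-replaced figures apply to escalation only, because Protocol 8.7.1 does not replace subjects in the confirmation cohorts.

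Three stronger readings are not supported:

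- A reader might infer that bleeding at low platelet counts generally escapes the DLT count. It does not: Grade 3 or hospitalized bleeds, repeated transfusions and long delays are covered.
- A reader might infer a large distortion of the MTD. That needs an event rate of several percent, for which the documents give no basis and which the covered routes make unlikely.
- A reader might infer that a prophylactic transfusion alone qualifies in the upper band. The criterion already requires significant bleeding.

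The sponsor should consider correcting the wording; the point does not undermine the design.

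**What to change.** In Protocol 8.5 and the synopsis, for both POM and LEN, apply the significant-bleeding criterion to all platelet counts below 50,000/µL. Keep the requirement of more than one platelet transfusion as an additional, separate criterion below 25,000/µL (POM) or 30,000/µL (LEN). The thresholds, cohort sizes and visits stay as they are.

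The change touches two bullets per combination in each place and needs a protocol amendment with ethics approval (Protocol 16.1). It has two costs. The DLT count will be slightly higher. And the affected subjects will stop study drug instead of having LEN or POM held and stepped down, as already happens for the same bleed at a higher count.
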